| 9.1. Adverse Events | 19 |
| 9.2. Other Safety Parameters..... | 21 |

| | |
|--|----|
| 10. Software Used for Analysis | 22 |
| 11. Changes from the Protocol..... | 22 |
| 12. Requirements and Specifications (Mock-shells) for Programming and Presentation of Tables, Listings and Figures (TLFs)..... | 22 |

This figure consists of a series of horizontal bars of varying lengths and positions, arranged in a descending staircase pattern from top-left to bottom-right. The bars are white on a black background. Some bars have small vertical tick marks at their ends. The bars are arranged in a descending staircase pattern from top-left to bottom-right.

[figure not shown]
This figure is a 2D grayscale heatmap representing a complex, multi-peaked distribution. The distribution is elongated horizontally, with several peaks of varying intensities. The background is dark, and the peaks are represented by lighter gray shades. The distribution is centered around the middle of the image, with a primary peak on the right side and a secondary, smaller peak on the left side. The overall shape is roughly rectangular but with irregular, jagged edges, suggesting a noisy or high-resolution data set.

List of Abbreviations

| | |
|--------|--|
| ADaM | Analysis Data Model |
| AE | Adverse Event |
| ATC | Anatomical Therapeutic Chemical |
| BCVA | Best Corrected Visual Acuity |
| CI | Confidence Interval |
| CRF | Case Report Form |
| CSR | Clinical Study Report |
| DDD | Defined Daily Dose |
| EDC | Electronic Data Capture |
| GCP | Good Clinical Practice |
| ICH | International Conference on Harmonization |
| IMP | Investigational Medicinal Product |
| IOP | Intraocular Pressure |
| ITT | Intent to Treat |
| LOCF | Last Observation Carried Forward |
| MedDRA | Medical Dictionary for Regulatory Activities |
| OD | Right Eye |
| OS | Left Eye |
| OTC | Over The Counter |
| PP | Per Protocol |
| PT | Preferred Term |
| SAE | Serious Adverse Event |
| SAP | Statistical Analysis Plan |
| SD | Standard Deviation |
| SDTM | Study Data Tabulation Model |
| SOC | System Organ Class |
| SOP | Standard Operating Procedure |
| TEAE | Treatment Emergent Adverse Event |
| TLFs | Tables, Listings, and Figures |
| WHOCC | World Health Organization Collaborating Center |

1. Administrative Structure

1.1. Study Sponsor

1.2. Introduction and Scope

This Statistical Analysis Plan (SAP) provides detailed statistical methodology for the analysis of data from protocol number AG-920-CS301, Version 1.0 (09-Jun-2020) that will be presented in the Clinical Study Report (CSR). The variables and methods described in this plan supersede those described in the protocol. Any deviations from the analyses described in the final SAP will be noted in the CSR.

The SAP may also serve as a reference for the creation of any outputs required outside of the CSR, e.g., abstracts, posters, presentations, manuscripts and management updates. Data used for these analyses will have a status aligned to the database lock guidance.

The statistical analyses will be done in accordance with the ICH-E9 guidelines “Statistical Principles for Clinical Trials” and applicable local guidelines.

1.3. Responsibility of Data Management Team

The responsibility of providing clean data for the statistical analysis lies with TAB Clinical Data Management team. The Data Management team has designed the eCRF in the Castor EDC system, version 2020.2.8, in order to perform data capture, data review and data cleaning including a query management process. The data review, cleaning and locking are described in detail in the Data Management Plan and the related SOPs.

1.4. Responsibility of SAS Programmer or Statistician

SAS programmers or statisticians will be responsible for programming the statistical tables, listings and figures (TLFs), as well as the ADaM/STDM datasets as per the approved SAP for the study clinical data.

2. Study Objectives and Endpoints

2.1. Study Objectives

Primary Objective:

- To evaluate anesthetic efficacy of AG-920

Secondary Objectives:

- To evaluate how long it takes one dose of AG-920 to anesthetize the eye
- To evaluate how long one dose of AG-920 anesthetizes the eye
- To evaluate the safety and tolerability of AG-920

2.2. Endpoints

Primary Endpoint

- The proportion of patients with no pain at 5 minutes

Secondary Endpoints

- The proportion of patients with no pain within 5 minutes
- Mean time to no pain score (onset)
- Mean duration of anesthetic effect
- Visual acuity, biomicroscopy, adverse events (AEs), treatment-emergent adverse events (TEAEs), serious AEs (SAEs), withdrawals due to TEAEs

3. Study Design

3.1. Overall

A brief description of the study design and activities is provided below. For detailed information, refer the study design section of the protocol.

This is a randomized, placebo-controlled, double-masked, parallel-group study to evaluate the local anesthetic effect of [REDACTED] Sterile Topical Ophthalmic Solution in healthy volunteers. The study will consist of one or two clinic visits and one follow-up phone call. Subjects will be screened for entry at Visit 1 and randomized/treated at Visit 2. Visit 1 and 2 may be on the same day. The subjects will be randomized in a 1:1 ratio to receive a single dose of either AG-920 or Placebo (vehicle) in one (study) eye. The study eye will be randomized as either the right eye (OD) or the left eye (OS). The single dose will be administered by the clinic staff as two drops in the study eye 30 seconds apart. All ocular assessments at Visits 1 and 2 will be performed on both eyes. Subjects will then have a safety follow-up phone call 1-4 days following Visit 2 (Study Day 2-5).

Approximarely 120 subjects are planned to be enrolled to ensure 60 in each treatment group.

3.2. Sample Size

With 60 subjects per treatment group and assuming a 15% response in the vehicle group for the primary endpoint, this study will have 88% power to detect a treatment effect of at least 25% (40% vs. 15%) between AG-920 and placebo. This is based on a two-sample chi-square test and assuming a two-sided Type I error rate (α) of 0.05.

3.3. Investigational Products

[REDACTED] Sterile Topical Ophthalmic Solution (AG-920) is a sterile, isotonic, non-preserved aqueous solution containing the active ingredient [REDACTED] Boric Acid, Mannitol, Sodium Acetate Trihydrate, Glacial Acetic Acid, and Edetate Disodium Dihydrate. [REDACTED]
[REDACTED]

Placebo ophthalmic solution is identical to the active product, with the exception of the active ingredient.

3.4. Randomization

A randomization code for allocating the treatments will be prepared by an independent biostatistician, who is not involved in the day-to-day conduct of the study. Subjects will be randomized in a 1:1 ratio to receive AG-920 or Placebo.

Treatment assignments will be masked to the Investigator, the clinical study team (Sponsor, personnel involved in day to day study management, Monitors, Data Managers, and Statisticians), and the subjects. Only in the case of medical emergency or occurrence of adverse events that warrant unmasking in the opinion of the Investigator, will the treatment assignment(s) be unmasked and made available to the Investigator and the Sponsor Safety Officer. In the absence of medical need, the randomization code will not be available to the above personnel until after the study is completed and the database is locked.

3.5. Post Treatment and Pinch Test

[figure not shown]
A [REDACTED] forceps will be used to “pinch” the inferior bulbar conjunctiva of the study eye at the [REDACTED]

As soon as the subject does not experience pain [REDACTED] pinching will stop until the 5-minute timepoint [REDACTED]

Within 15-60 minutes after the last pinch test, the following examinations will be performed:

- Best corrected visual acuity (BCVA)
- Slit lamp biomicroscopy and external eye exam
- Assessment for adverse events

3.6. Study Schedule

| | Visit 1 | Visit 2 | | | | | Phone Follow-Up |
|---|----------------------|---------------------------------|---------------|------------|------------|------------|--------------------------------|
| | Screening | Screening & Baseline | | | | | |
| | Day -2 to 0/1 | Day 1¹ | | | | | Day 2-5 |
| | Pre-dose | Dose | | [REDACTED] | [REDACTED] | 5 m | 15-60 m post last pinch |
| Procedures | | 0 sec | 30 sec | | | | |
| Written Informed Consent | X | | | | | | |
| Inclusion/Exclusion Criteria | X | X | | | | | |
| Demographics, Systemic and Ocular Medical History | X | | | | | | |
| Concomitant Medication Query | X | X | X | | | | X |
| OTC Tear Tolerability | X | | | | | | |
| BCVA | X | | | | | | X |
| Urine Pregnancy Test (if applicable) | X | | | | | | |
| Biomicroscopy and External Eye Exam | X | | | | | | X |
| IOP Measurement | X | | | | | | |
| Randomization | | X | | | | | |
| IMP Administration ² | | X | X | | | | |
| Conjunctival pinch ³ | | | | X | X | X | X |
| Assessment of Pinch Pain | | | | X | X | X | X |
| Adverse Event Assessment | | X | X | X | X | X | X |

BCVA = Best corrected visual acuity, IOP = Intraocular pressure, OTC = over the counter, IMP = investigational medicinal product.

¹ Screening may occur on the same day as Visit 2 (≥ 60 minutes) or up to 3 days previously. If on separate days, inclusion/exclusion criteria will be re-evaluated prior to dosing subject to ensure subject still qualifies.

² One dose is 2 drops. First drop administered at 0 seconds and the second drop administered at 30 seconds (2 drops 30 seconds apart).

³ [REDACTED]

4. Analysis Sets

4.1. Randomized Population

The randomized population will include all subjects who are randomized to treatment. Baseline (screening) variables and demographic characteristics will be summarized for this population.

4.2. Intent-to-Treat (ITT) Population

The ITT population will include all randomized subjects who have received at least one dose (drop) of study medication. This population will be the primary population for the efficacy analyses and all efficacy variables will be summarized using this set of subjects. The ITT population will include all subjects as randomized, even if there are subjects who are given the wrong study medication.

4.3. Per-Protocol (PP) Population

The PP population is a subset of the ITT population, which will include those subjects (and their visits) who do not have major protocol violations likely to seriously affect the primary outcome of the study as judged by a masked evaluation prior to the unmasking of the study treatment. This population will be the secondary population for the efficacy analyses and all efficacy variables will be summarized using this set of subjects. If the PP and ITT populations are exactly the same and there are no missing data, then additional efficacy analyses on the PP population will not be performed. The PP population will include subjects as treated, so if there are subjects who are given the wrong study medication, then they will be included in the treatment group based on what they received.

4.4. Safety Population

The Safety population will include all randomized subjects who have received at least one dose (drop) of study medication. This population will be used to summarize the safety variables and will include all subjects as treated.

5. General Aspects of Statistical Analysis

All TLFs will be independently checked for consistency, integrity and in accordance with the applicable SOP(s). The shells for the TLFs are presented in a separate document.

5.1. Presentation of Summaries and Analyses

In general, continuous data will be summarized by descriptive statistics, i.e., n, mean, standard deviation (SD), median, minimum and maximum values, and categorical data will be summarized using counts (N: number of subjects per treatment group, n: number of subjects with non-missing values) and percentages. Percentages will be suppressed when the count is zero, however the category will still be displayed. The denominator for all percentages will be the number of subjects per treatment in the analysis set of interest (%: n/N*100), unless otherwise indicated.

In general, and unless specified otherwise, all data summaries will be sorted by the parameter under consideration and then by visit. Listings will be sorted as per subject ID, the parameter under consideration and then by visit.

Unless otherwise stated, baseline will be defined as the last value of the assessment recorded prior to first study drug administration.

5.2. Precision of Display

Means and medians will be rounded off to one decimal place more than the reported data values. Standard deviations will be rounded off to two decimal places more than the reported data values. Minimum and maximum values will be of the same precision as that of the reported data.

The precision of display for the variables will be up to one decimal place for percentage values, e.g., xx (xx.x), where the value inside the parentheses represents the percentage value. Counts (n) will be displayed as integers.

All *P* values will be reported based on two-sided significance tests and all *P* values less than or equal to 0.05 (≤ 0.05) will be considered statistically significant. *P* values will be reported to four decimal places or as <0.0001 .

5.3. Strategy of Pooling the Data Across Centers

Not applicable for this single-site study.

5.4. Coding Dictionaries

The Medical Dictionary for Regulatory Activities (MedDRA) version 23.0 or higher will be used to code the adverse events and medical history. The World Health Organization Collaborating Center (WHOCC) Anatomical Therapeutic Chemical/Defined Daily Dose (ATC/DDD) Index 2020 classification system will be used to code the concomitant medications.

5.5. Handling of Missing/Partial Dates for Adverse Events

Because of the short duration of the study and only a single dose of study drug being given, missing or partial start or end dates for AEs are not expected. Therefore, the duration of most AEs should be able to be calculated. If there is a missing or partial start or end date for an AE, then the duration of that event will be missing.

Missing or partial dates will be listed in the subject data listing as they appear in the database.

5.6. Handling of Data from Unscheduled Visits

Data from unscheduled visits will only be displayed in subject data listings and will not be used in calculating summary statistics. However, if AEs occur or are reported during an unscheduled visit then those will be summarized.

6. Subject Disposition

The following subject disposition details will be summarized by treatment group and overall and listed to include the number and percentage of subjects:

- Informed Consent signed
- Screened
- Screened Failure
- Dosed or did not initiate treatment
- Completed the study as per protocol
- Discontinued study
- Withdrawn from the study
- Included in each analysis set

These data will also be listed. Individual reasons for withdrawal will be presented in listings for all enrolled subjects.

7. Demographic and Baseline Measurements

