3.6.5 Actions after discontinuation

All subjects who discontinue IMP due to a report of an AE **must** be followed-up and provided appropriate medical care until their signs and symptoms have remitted, stabilized, determined to be chronic, or until abnormal laboratory findings have returned to acceptable or pre-study limits.

For the subject who chooses to withdraw consent or who is non-compliant, every possible effort should be made by the Investigator to assure there is a final visit that includes all examinations listed for Visit 2.

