6.5 Follow-Up Phone Call (Day 2-5)

Subjects will receive a phone call from site staff between Days 2-5, which is 1-4 days (24-96 hours post-dose) following treatment with IMP. Subjects will be asked about

- AEs
- Changes to concomitant medications

If there are any ongoing adverse events, the subject will be instructed to return to the investigator's office for appropriate evaluation. If there are no ongoing adverse events, the subject will be considered completed.

Subjects will be thanked for their participation and released to follow their normal standard of care.

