6.6 Unscheduled visits

To ensure subject safety during the trial, any subject who requires additional follow-up during the study for any reason (that does not fall on a scheduled study visit) should have that visit recorded as an Unscheduled Visit.

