9.2. Other Safety Parameters

Best corrected visual acuity and slit lamp biomicroscopy will be measured at Visit 1 (screening) and at the end of Visit 2. BCVA will be measured in logMAR units and results will be summarized using descriptive statistics for the Visit 1 and Visit 2 values and for the changes from Visit 1 to Visit 2. Results will be presented separately for the study eye and non-study eye.

The biomicroscopy grading scales are given in Appendix 1 of the protocol; the following assessments will be done on four anterior locations of each eye:

- Lid (erythema and edema)
- Conjunctiva (hyperemia and edema)
- Cornea (edema)
- Anterior chamber (cells and flare)

The data for each assessment will be summarized using counts and percentages of eyes within each category and will be summarized for the Visit 1 and Visit 2 values and for the changes from Visit 1 to Visit 2. Results will be presented separately for the study eye and non-study eye.

10. Software Used for Analysis

SAS Software Version 9.4 or higher (SAS Institute Inc., Cary, NC), will be used for the statistical analysis and statistical reporting.

11. Changes from the Protocol

The variables and methods described in this plan will supersede those described in the protocol.

12. Requirements and Specifications (Mock-shells) for Programming and Presentation of Tables, Listings and Figures (TLFs)

This document is intended to be used only as a guide in the development of TLFs and may be adjusted to meet study and Sponsor specific needs.

The specifications for the TLFs must follow the description in the associated Statistical Analysis Plan (SAP).

The following details the requirements and specifications for the programming and presentation of the TLFs, as set out in the TLF shells.

- A separate RTF document will be created for each TLF.
- All TLFs will be produced in a landscape format, as far as is feasible.
- The margin, page size specifications are stipulated below and will be used for the presentation of all TLFs:

| Item: | Specification: |
|--------------------|----------------|
| Page Layout | Landscape |
| Paper Size | 8.5 x 11 inch |

- The standard font size and font type are "9 point", "Courier New" for all TLFs.
- Every page of each output will have a header indicating the Sponsor name and protocol number (to be presented as set out in the example below).

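### Eye exams done at off-schedule recall visits are confined to listings, so the BCVA and biomicroscopy tables cannot show a finding made after Visit 2

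*SAP*

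**What the plan says.** SAP 5.6 sets the rule: "Data from unscheduled visits will only be displayed in subject data listings and will not be used in calculating summary statistics". The next sentence gives the one exception: "However, if AEs occur or are reported during an unscheduled visit then those will be summarized".

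SAP 9.2 names two time points for BCVA and biomicroscopy, screening and the end of Visit 2. The biomicroscopy data "will be summarized for the Visit 1 and Visit 2 values and for the changes from Visit 1 to Visit 2", with study eye and non-study eye shown separately. BCVA is handled the same way with descriptive statistics in logMAR.

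Two kinds of visit fall outside the schedule tables (Protocol Table 1, SAP 3.6), whose only contacts are Visit 1, Visit 2 and a phone call:

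- Recall after the call. Protocol 6.5: "If there are any ongoing adverse events, the subject will be instructed to return" to the office to be evaluated. Under Protocol 6.6, a subject who needs extra follow-up away from a scheduled visit "should have that visit recorded as an Unscheduled Visit".
- Exit after withdrawal of consent or non-compliance. Protocol 3.6.5 says that "every possible effort should be made by the Investigator to assure there is a final visit that includes all examinations listed for Visit 2". It calls this a final visit and does not say under which visit label it is recorded.

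On percentages, SAP 5.1 sets a default: "The denominator for all percentages will be the number of subjects per treatment in the analysis set of interest". That default gives way where the SAP indicates something else.

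**The concern.** Visual acuity and biomicroscopy are named endpoints in Protocol 2 and SAP 2.2. The only scheduled post-dose eye exam comes 15 to 60 minutes after the last pinch, on the day of dosing. Follow-up after that is by telephone. A corneal, conjunctival or acuity change that appears or worsens later can therefore be measured only at an off-schedule visit, and SAP 5.6 keeps exactly those measurements out of the tables. A recalled subject whose Visit 2 exam was normal would appear in the BCVA and biomicroscopy tables with the normal value only.

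Protocol 9.4.7 is worded more broadly. It has biomicroscopy summarized at every time point measured and visual acuity at each time point. SAP 1.2 and 11 say that the SAP supersedes the protocol, but SAP 11 does not mention this narrowing.

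The stake is how completely two safety tables describe the eye after dosing. The primary analysis, alpha and power are not involved.

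**Working it through.** No figure in the plan is in dispute here, so the check is mainly one of reading the rules together.

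**1. Recall visit.**
- Protocol 6.5 creates the visit, and neither schedule table contains it.
- Protocol 6.6 therefore records it as unscheduled.
- SAP 5.6 restricts its data to listings, adverse events excepted.
- SAP 9.2 has no row after Visit 2.
- Any BCVA or slit-lamp result from the visit is thus listed and not summarized. This follows directly from the text.

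**2. Final visit on early exit.**
- Protocol 3.6.5 asks for the Visit 2 examinations.
- If the visit is entered as unscheduled, step 1 applies to it.
- If it is entered as Visit 2, SAP 9.2 would summarize it, but a later exam would then sit unmarked among same-day exams.
- Neither document chooses, so the outcome is open.

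**3. What the adverse event tables carry.** SAP 9.1 summarizes treatment-emergent events by system organ class and preferred term, and by causality and severity. Those tables contain no logMAR change and no biomicroscopy grade, so they overlap with the SAP 9.2 tables without replacing them.

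**4. Scale of one missing finding.** Input: 60 per arm (Protocol 9.2, SAP 3.2). Number of affected subjects: not given in either document; 1 to 3 per arm is assumed for illustration.

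- One subject: 1/60 = 1.7 percentage points.
- Three subjects: 3/60 = 5.0 percentage points.

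To show what such a difference means at this sample size, take the two-sided 95% Clopper-Pearson upper limit. For 0 events it is 1 − 0.025^(1/60). For k events it is the p that solves P(X ≤ k | 60, p) = 0.025.

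| Subjects with a finding | Observed | Upper limit |
|---|---|---|
| 0 of 60 | 0.0% | 5.96% |
| 1 of 60 | 1.7% | 8.94% |
| 2 of 60 | 3.3% | 11.53% |

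SAP 9.2 plans no intervals for these tables, so the limits only illustrate scale.

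**5. Denominator.** Suppose m of 60 eyes have no Visit 2 exam and the SAP 5.1 default applies. Each abnormal percentage is then multiplied by (60 − m)/60.

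- m = 1: 59/60 = 0.983, a relative reduction of 1.7%.
- m = 3: 57/60 = 0.95, a relative reduction of 5%. For example, 6 abnormal eyes would read 6/60 = 10.0% against 6/57 = 10.5% of eyes examined.

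The effect is small. It concerns biomicroscopy only, because SAP 9.2 gives BCVA no percentages.

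**The case against.** The strongest reply is that the signal is not lost. Protocol 8.3.1 counts an abnormal sign as an adverse event, and Protocol Appendix 1 treats a three-line acuity change as clinically significant. A subject recalled for an ongoing event already has a treatment-emergent event, and SAP 5.6 keeps events from unscheduled visits in the by-arm summaries. The eye values themselves remain in the listings. This stands. A reader who stops at the first sentence of SAP 5.6 might infer that unscheduled-visit data vanish from all summaries; the next sentence rules that out.

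Second, a recalled subject would normally have had the Visit 2 exam already, and Protocol 6.5 prescribes neither BCVA nor biomicroscopy at recall. There may be few such values, or none. SAP 8 expects little missing data on Day 1. This also stands, and it limits the size of the point.

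Third, a reader might infer that the exit exam is certain to be excluded. The documents do not say so. It is called a final visit, it is asked for on a best-effort basis, and it concerns only consent withdrawal and non-compliance.

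Fourth, it is tempting to say that a subject without an exam is shown as having no finding. That does not follow: such a subject is counted in no grade, so the categories add to less than N, and SAP 5.1 reports the number of non-missing values. What remains is the small dilution in working step 5. Even that depends on whether SAP 9.2's reference to percentages of eyes already overrides the default, which it does not make clear.

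Finally, Protocol 9.5 bases the Safety population on observed data. That sentence rules out imputation; it does not require every off-schedule value to enter a by-visit table. The time-point wording in Protocol 9.4.7 can likewise be read as meaning scheduled time points, so the difference from the SAP is a narrowing to be explained, not a flat contradiction.

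**Conclusion.** The point holds in limited form. For recall visits, the rules in SAP 5.6 and 9.2 set aside any observed post-dose BCVA or biomicroscopy value from these two summaries. For the Protocol 3.6.5 final visit the same follows only if it is recorded as unscheduled, and that is unsettled.

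The consequence is a possible understatement of ocular findings in two tables. It might be inferred that the safety results are biased toward no harm, or that the loss differs by arm. The documents do not support either: the related adverse event is tabulated by arm, no count of affected subjects is given, and nothing in the plan indicates unequal recall or exit. At 60 per arm the size is 1.7 percentage points per affected subject, under the assumption that an eye exam was done at that visit and was worse than the Visit 2 exam. Severity is low; the reason to act is that the remedy costs almost nothing.

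**What to change.** Amend SAP 5.6 and 9.2 before unmasking:

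1. Keep the Visit 1, Visit 2 and change tables as planned. Add a worst post-dose row, by arm and by study and non-study eye, for BCVA change from baseline and for each biomicroscopy grade. Take it over all post-dose exams, including the Protocol 3.6.5 final visit and any unscheduled visit, and flag values from those visits with time since dose. This makes the row independent of how the final visit is labelled.
2. State that biomicroscopy percentages use the number of eyes examined, in place of the SAP 5.1 default.

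A later exam should not be moved into the 15-60 minute slot, because that would mix time points in the by-visit table. Record in SAP 11 how the result differs from Protocol 9.4.7.

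Cost: SAP wording, shell changes and one added row per parameter. No new visits or data are needed. The downside is small: the worst post-dose row mixes exam times, and subjects examined more often have more chances of a poor value, so the row should stay descriptive and carry the time flag.
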